## 1. Protocol Synopsis

### Title of Study:

A Phase 1 Randomized, Placebo-Controlled Study of LY3316531 in Healthy Subjects and an Open-Label, Single-Dose Study in Patients with Psoriasis

### Rationale:

LY3316531 is a humanized bispecific antibody that selectively binds to interleukin-23 and calcitonin gene-related peptide (CGRP). This dual inhibitor is an innovative attempt to target pathways that affect the pathology associated with auto-inflammatory conditions.

This first-in-human study will explore the safety, tolerability, and pharmacokinetics (PK) of single and multiple doses of LY3316531 in healthy subjects and the safety, tolerability, PK, and pharmacodynamics (PD) of a single dose of LY3316531 in patients with psoriasis.

### Objective(s)/Endpoints:

Objectives	Endpoints
Primary 
 
To explore the safety and tolerability of single and multiple doses of LY3316531 in healthy subjects
 
To explore the safety and tolerability of a single dose of LY3316531 in patients with psoriasis
 
	Incidence of adverse events, treatment-emergent adverse events, and serious adverse events
Secondary 
 
To characterize the PK of LY3316531 following IV and SC administration in healthy subjects
 
To characterize the PK of LY3316531 following IV administration in patients with psoriasis
 
	$C_{max}$ and AUC

Abbreviations: AUC = area under the concentration versus time curve;  $C_{max}$  = maximum observed drug concentration; IV = intravenous; PK = pharmacokinetics; SC = subcutaneous.

### Summary of Study Design:

Study I9H-MC-FFAA is a multicenter, randomized, sponsor unblind, subject- and investigator-blind (investigator will be partially blind for Cohorts 1 and 2 and unblind for cohort 5 in Part A), placebo-controlled, parallel-dose group, single-ascending dose design in healthy subjects (Part A), multiple-dose design in healthy subjects (Part B), and an open-label, single-dose design in patients with psoriasis (Part C).

### Treatment Arms and Planned Duration for an Individual Patient/Subject:

**Part A (Single-Ascending Dose [SAD] in Healthy Subjects):** After a screening period up to 28 days, eligible subjects will be randomized to receive a subcutaneous (SC) or intravenous (IV) dose of LY3316531 (3 mg IV, 15 mg IV, 75 mg IV, 300 mg IV, 300 mg SC, 900 mg IV, or 2000 mg IV [planned dose]) or placebo (IV) on the morning of Day 1. Subjects will remain in the CRU for 24 hours after study drug administration and attend scheduled visits at the CRU for 12 weeks to assess the measurements for safety, tolerability, and PK. Sentinel dosing for the first 2 subjects of Cohorts 1 and 2 will be performed with 1 subject receiving LY3316531 and the other receiving placebo in a blinded manner.

**Part B (Multiple-Dose in Healthy Subjects):** After a screening period up to 28 days, eligible subjects will be randomized to receive a planned IV dose of LY3316531 (2000 mg [planned dose]) or placebo on the morning of Days 1, 29, and 57. The planned dose of 2000 mg LY3316531 may be adjusted based on safety, PK, and target-engagement data obtained in Part A of the study. An optional SC or IV second multiple-dose cohort will be determined after reviewing the data from the first cohort.

Subjects will remain in the CRU for 24 hours after receiving each dose of study drug and attend scheduled visits at the CRU for 12 weeks following the final (third) dose of LY3316531 to assess the measurements for safety, tolerability, and PK.

**Part C (Single-Dose in Patients with Psoriasis):** After a screening period up to 35 days, eligible patients with psoriasis will be enrolled to receive a single dose of LY3316531 on the morning of Day 1. Patients will receive 300 mg IV in Cohort 1 or, in the 2 optional cohorts, receive either a SC or IV dose (to be determined) not to exceed the maximum tolerated dose in Part A or the highest dose previously evaluated in healthy subjects. Patients will remain in the CRU for 24 hours after study drug administration and attend scheduled visits at the CRU for 16 weeks following administration of the study drug to assess the measurements for safety, tolerability, PK, and PD. Patients who respond to LY3316531 therapy will enter an extended follow-up period, which requires monthly visits up to Week 52. Patients who enter the extended follow-up period should be discontinued from the study when additional therapy becomes necessary (as determined by the investigator and patient).

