### 3.3. Benefit/Risk Assessment

The nonclinical safety information for LY3316531 supports the transition from preclinical status to a clinical, first-in-human study. On the basis of the nonclinical data, LY3316531 is not considered to be a high-risk compound. This protocol reflects the fact that LY3316531 has not been administered to humans previously, and to mitigate this risk, the study has been designed to be conducted in accordance with principles outlined in the Guideline on Strategies to Identify and Mitigate Risks for First-in-Human Clinical Trials with Investigational Medicinal Products. Any identified risks are considered to be monitorable and manageable at the planned dose range with starting dose of 3 mg up to a maximum dose not to exceed 2000 mg for LY3316531 in healthy subjects and patients with psoriasis.

There is no anticipated therapeutic benefit for the healthy subjects. There is a potential for patients with psoriasis to experience some level of therapeutic benefit during this study, as blockade of IL-23 is known to improve psoriasis.

More information about the known and expected benefits, risks, serious adverse events (SAEs) and reasonably anticipated adverse events (AEs) of LY3316531 are to be found in the Investigator's Brochure (IB).

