**Table FFAA.5.1. Summary of Maximum Number of Patients/Subjects per Cohort**

Cohort #	Planned Dose/ Administration Route	Number of Planned Subjects		Total Number of Planned Subjects
		LY	PBO	
Part A				
SAD Cohort 1 a	3 mg/IV	3	1	4
SAD Cohort 2 a	15 mg/IV	3	1	4
SAD Cohort 3	75 mg/IV	6	2	8
SAD Cohort 4	300 mg/IV	6	2	8
SAD Cohort 5	300 mg/SC	6	0	6
SAD Cohort 6	900 mg/IV	6	2	8
SAD Cohort 7	2000 mg/IV	6	2	8
Part B				
Multiple-Dose Cohort 1	2000 mg/IV	6	2	8
Multiple-Dose Cohort 2 b	Route and dose TBD	6	2	8
Part C				
Patient Cohort 1 c	300 mg/IV	8	0	8
Patient Cohort 2 b,c	Route and dose TBD	8	0	8
Patient Cohort 3 b,c	Route and dose TBD	8	0	8

Abbreviations: IV = intravenous; LY = LY3316531; PBO = placebo; SAD = single-ascending dose; SC = subcutaneous; TBD = to be determined.

a Sentinel dosing will be used in this cohort.

[figure not shown]
b Optional subject or patient cohort. Actual dose and route of administration will be determined based on cumulative data from previous cohorts, but will not exceed 2000 mg of LY3316531 administered IV.

c A minimum of 7 patients are planned but up to 8 patients are allowed per cohort.

A follow-up visit will be performed according to the Schedule of Activities (Section 2).

Study governance considerations are described in detail in [Appendix 3](#).

[Figure FFAA.5.1](#) illustrates the study design.

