### **5.1.3. Part C (Single-Dose Design in Patients with Psoriasis)**

One planned single-dose cohort will be enrolled to receive IV administration of LY3316531 with the option of 2 subsequent cohorts where the dose levels and route of administration (SC or IV) would be determined after reviewing the data from the first IV cohort.

The first cohort is planned to receive 300 mg of LY3316531 pending the analysis of available safety data from Part A. The safety scenarios for AEs, SAEs, and adverse laboratory abnormalities described in Section 7.4.2 that would prevent dose escalation in Parts A and B are the same that would prevent initiation of Part C. The actual starting dose and expected exposure will not exceed the dose/exposure that is concurrently being evaluated in Part A. Any available preliminary PK data from Cohorts 1, 2, and 3 (through Day 29) in Part A will be considered in the decision to initiate Part C as well.

Similarly, the dose for the optional cohorts will be determined based on cumulative data from previous cohorts, but will not exceed 2000 mg of LY3316531. Section 7.4.1 provides detailed information on how dose levels for the 2 optional cohorts will be determined and when the cohorts will begin enrollment procedures.

All patients who respond to LY3316531 treatment by exhibiting at least 50% reduction from baseline Psoriasis Area and Severity Index (PASI) score at Week 12 (Visit 11; Day 85) can enter an extended follow-up period for up to 52 weeks post-treatment administration (see Section 2.3). Other subjects who do not meet the above criterion for PASI reduction should be considered for discontinuation from the study at Week 16 (Visit 12; Day 113). Exceptions could be considered after a discussion between the sponsor and investigator.

A patient's participation is considered as complete if he/she received the study drug and completes all activities up to and including at least Day 85. Patients may be replaced if PK or PD data are not collected up to and including Day 85.

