## 5.5. Justification for Dose

The wide dose range selected for Part A of the study is based on PK and efficacy data available from clinical studies with the IL-23 monoclonal antibody (mAb) (CCI [REDACTED]) and the CGRP mAb (CCI [REDACTED]), coupled with preclinical PK information for LY3316531 in cynomolgus monkeys and relative potency information collected in humanized IL-23 mouse PD model experiments. The planned starting dose of 3 mg IV is expected to have minimal biological activity and the maximum dose of 2000 mg IV is expected to support the highest doses that may be evaluated in the multiple-dose and Phase 2 studies. CCI [REDACTED]

The starting and maximum doses are expected to produce AUCs that are 851 and 5 $\times$  lower, respectively, than the AUC observed at the NOAEL dose in toxicology studies in cynomolgus monkeys (Table FFAA.5.2).

The dose(s) for Parts B and C will be selected based on available PK and safety data from Part A of the study. The highest dose that may be evaluated in Part B will not exceed the maximum tolerated dose (MTD) in Part A. In the event PK data from Part A indicate that significant drug accumulation is likely to occur with doses of 2000 mg LY33165314 administered every 4 weeks, the dose administered in Part B will be reduced.

The doses for Part C will also be selected based on data from Part A of this study and the single-dose study with CCI in patients with psoriasis, and will be selected to allow for comparative exposure-response analyses between LY3316531 and CCI using psoriasis efficacy measures.

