### 7.4.2. Dose Escalation (Parts A and B)

By nature of being a dose-escalation study, data will be evaluated on an ongoing basis. The highest dose level that is tolerated will be designated as the MTD.

Safety data will be the primary criteria for the dose escalation. In addition, if available at the time of dose-escalation decision, PK results ( $C_{max}$  and AUC) will be used as supporting data for dose escalation, but such data are required only for Cohort 1 in Part B. No dose decision can occur without prior discussion and agreement between the investigator and the Lilly clinical pharmacologist or CRP.

Prior to dose escalation, a safety review meeting will be undertaken by the sponsor (unblinded) and the investigator (blinded) to evaluate the safety data and agree on the appropriate dose for the next cohort. Emerging PK data (if available) may inform dose selection for the higher dose levels, based on planned PK preliminary analyses after SAD Cohort 3 (Part A). If considered appropriate, previous dose levels may be repeated, or lower/intermediate dose levels may be

tested. The magnitude of the dose escalation may be reduced after data review, but subsequent escalations cannot be increased by more than approximately 3-fold (a half-log increment).

For Cohorts 1 and 2 in Part A, the decision to escalate to the next cohort will occur when at least 15 days have elapsed after all subjects in the preceding cohorts have been dosed. In Cohorts 3, 4, 6, and 7, the decision to dose the next cohort will occur when all subjects in the preceding cohorts have been dosed and data for a minimum of 15 days are available from at least 7 subjects in the preceding cohort. If at the time of the trial level safety review for Cohort 4, data are also available from Cohort 5, all available data from Cohorts 4 and 5 will be considered in the review to dose the next cohort.

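### The dose ceiling for the optional psoriasis cohorts is stated inconsistently: Part A MTD or highest dose evaluated in the synopsis, 2000 mg alone in the body text and SAP

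*Protocol*

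**What the plan says.** The ceiling for the optional Part C cohorts, or a limit that bears on it, appears in several places.

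- **Protocol synopsis, Treatment Arms, Part C:** the optional dose is "not to exceed the maximum tolerated dose in Part A or the highest dose previously evaluated in healthy subjects".
- **Protocol 5.1.3:** "the dose for the optional cohorts will be determined based on cumulative data from previous cohorts, but will not exceed 2000 mg of LY3316531". SAP Section 5.3 says the same.
- **Protocol Table FFAA.5.1, footnote b:** the optional dose and route depend on cumulative data, "but will not exceed 2000 mg of LY3316531 administered IV". SAP Table 1 has the same footnote.
- **Protocol 3.3:** a study-wide "maximum dose not to exceed 2000 mg for LY3316531 in healthy subjects and patients with psoriasis".
- **Protocol 5.5:** "The highest dose that may be evaluated in Part B will not exceed the maximum tolerated dose (MTD) in Part A". For Part C it says only: "The doses for Part C will also be selected based on data from Part A of this study", together with data from a single-dose study of another agent in psoriasis.
- **Protocol 7.4.2:** "The highest dose level that is tolerated will be designated as the MTD".
- **Protocol 7.4.1 (Dose Decision, Part C):** available PK and applicable safety data from Part A are to be considered for the optional dose, and the 7.4.2 stopping scenarios apply. The visible text gives no ceiling, and part of the section is redacted.

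**The concern.** In the visible text, the limit tied to the MTD or to a dose already given to healthy subjects appears for Part C only in the synopsis. The sections that a team would open to choose an optional dose (5.1.3, Table FFAA.5.1 and the visible part of 7.4.1) do not repeat it.

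The synopsis wording is itself open to two readings. By the 7.4.2 definition, if Part A stops because a dose is not tolerated, the highest dose evaluated lies above the MTD, and the synopsis does not say that the lower of the two governs.

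The ceiling could come into play. The synopsis allows a higher optional dose if Cohort 1 shows little effect on PASI. This is a first-in-human trial, and the upper limit for patients should not depend on which section is read.

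**Working it through.** The plan has no calculated figure to reproduce here. The check is to ask what maximum dose each wording permits under different Part A outcomes.

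**Inputs.** Part A IV dose levels of 300, 900 and 2000 mg (Table FFAA.5.1); the MTD as the highest tolerated level (7.4.2); the 2000 mg limit (3.3, 5.1.3, Table FFAA.5.1). The Part A outcomes are assumptions, and before Part A ends the MTD is taken as the highest dose tolerated so far.

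**Readings.**

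1. Synopsis, exceed neither limit: min(MTD, highest dose evaluated, 2000).
2. Synopsis, permissive 'or': min(max(MTD, highest dose evaluated), 2000).
3. The 2000 mg text read alone: 2000.

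| Assumed Part A outcome | Reading 1 (mg) | Reading 2 (mg) | Reading 3 (mg) |
|---|---|---|---|
| 2000 mg given and tolerated | 2000 | 2000 | 2000 |
| 2000 mg given, not tolerated (MTD 900) | 900 | 2000 | 2000 |
| 900 mg given, not tolerated (MTD 300) | 300 | 900 | 2000 |
| 900 mg tolerated, 2000 mg not yet given | 900 | 900 | 2000 |
| 300 mg tolerated, 900 mg not yet given | 300 | 300 | 2000 |

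The three readings agree only if Part A reaches and tolerates 2000 mg. A dose not yet given in Part A is permitted only by reading 3. A dose not tolerated in Part A is permitted by reading 2 or reading 3.

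**Size.** In the third row, 900/300 = 3.0 and 2000/300 = 6.7. The optional cohorts hold up to 2 × 8 = 16 planned patients.

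**Can the decision fall before Part A is finished?** Part C opens on the Cohort 3 safety review, and an optional cohort needs at least 4 weeks of PASI data from at least 7 patients (7.4.1). Part A needs at least 15 days of data per step (7.4.2). Assume that Part A Cohort 4 and Part C Cohort 1, both at 300 mg IV, were dosed on the same day. The optional-cohort decision could then come from about 4 × 7 = 28 days. The 2000 mg cohort could start no earlier than about 15 + 15 = 30 days, after the steps to 900 and then to 2000 mg. Overlap is therefore possible on the protocol's own minimum intervals. Actual timing depends on enrolment, which the documents do not give.

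**The case against.** A reader might infer that the limits contradict each other, and that the protocol therefore lets patients be dosed above a level that Part A found not tolerated or had not tested. The documents do not support that.

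- All the limits are upper bounds, and one dose can satisfy every one of them. Section 3.3 shows that 2000 mg is the outer limit for the whole study; repeating it does not cancel the tighter synopsis limit.
- In ordinary usage, a dose that must not exceed A or B must exceed neither. The permissive reading is possible but is not the natural one.
- Part C is tied to Part A in other ways. The optional dose rests on cumulative data. Section 7.4.1 requires Part A safety data to be considered and applies the 7.4.2 scenarios. Section 5.1.3 says that those same scenarios would prevent Part C from starting. For the first cohort it adds: "The actual starting dose and expected exposure will not exceed the dose/exposure that is concurrently being evaluated in Part A".
- Section 7.4.1 and parts of 5.5 are redacted and the design figure is not shown, so one cannot say that no text links a Part A stop to the Part C dose.

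These points stand, and they limit the finding. They do not remove it. Data to be considered are inputs to a judgment, not a cap. The limit tied to the dose concurrently in Part A is written for the starting dose, not expressly for the optional cohorts. The statement about starting Part C does not say what a later Part A stop does once Part C is running. The limit of approximately 3-fold on escalation steps sits under Parts A and B in 7.4.2, and the visible text of 7.4.1 does not expressly bring it across.

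**Conclusion.** The ceiling for the optional Part C cohorts is inconsistently stated and, in the synopsis, ambiguous. The synopsis uses the MTD or the highest dose already evaluated; the body text, the cohort table and the SAP use 2000 mg only; the dose justification states an MTD cap for Part B only.

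A dose not yet given in Part A would be allowed only if the 2000 mg text were read without the synopsis. A dose not tolerated in Part A would be allowed only on that reading or on the permissive 'or'. On the assumed stop at 900 mg with an MTD of 300 mg, the ceilings are 300, 900 and 2000 mg. That spread is what the wording leaves open; it does not forecast what the sponsor would do. If Part A reaches and tolerates 2000 mg before the optional decision, the difference disappears. The conclusion rests on the visible text, and redacted wording in 7.4.1 could narrow it.

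**What to change.** Reconcile the protocol synopsis, Section 5.1.3, Table FFAA.5.1 footnote b and Section 5.5, with SAP Table 1 footnote b and SAP Section 5.3, so that each gives the same ceiling for the optional Part C cohorts. Reword the synopsis 'or' so that it is clear which limit governs when the MTD and the highest dose evaluated differ. Confirm that Section 7.4.1, including its redacted part, states how a stop in Part A bears on the optional Part C dose; if it does not, add a sentence.

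Which ceiling applies is a clinical decision for the sponsor and investigator, and none is proposed here. The change is to wording only, with no added patients, visits or procedures. Its one downside is some loss of freedom in choosing the optional dose.

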
#### **Number of Patients/Subjects:**

**Part A:** It is planned that up to 52 subjects may be enrolled in Part A of this study to obtain evaluable data from 46 subjects. The healthy subject SAD is planned to include 7 cohorts. Cohorts 1 and 2 are each planned to have 4 subjects (3 LY3316531:1 placebo), whereas Cohorts 3, 4, 6, and 7 are each planned to have 8 subjects (6 LY3316531:2 placebo). Cohort 5 is planned to have 6 subjects, all receiving LY3316531.

**Part B:** It is planned that up to 20 subjects may be enrolled in Part B of this study to obtain evaluable data from 16 subjects (total number of subjects for planned and optional cohorts). The healthy subject multiple-dose part of the study is planned to include up to 2 cohorts (2000 mg IV cohort with the option for 1 additional cohort) with 8 subjects per cohort (6 LY3316531:2 placebo).

**Part C:** It is planned that up to 30 patients may be enrolled in Part C of this study to obtain evaluable data from up to 24 patients (total number of patients for planned and optional cohorts). The patients with psoriasis single-dose part of the study is planned to include up to 3 cohorts (300 mg IV cohort with the option for 2 additional cohorts) with a minimum of 7 patients planned but up to 8 patients allowed per cohort (8 LY3316531). The decision to initiate enrollment in the optional cohorts will be based on the clinical activity, safety, and tolerability of LY3316531 as observed in Cohort 1. For example, a lower dose of LY3316531 may be investigated if the dose used in Cohort 1 is highly efficacious, based on the clinical activity measurement (Psoriasis Area and Severity Index

[PASI] scores), or if safety concerns arise. Conversely, a higher dose may be explored in an optional cohort if it is determined that LY3316531 had minimal effect on PASI scores.

**Statistical Analysis:**

**Safety:** All investigational products (IPs) and protocol procedure adverse events will be listed, and if the frequency of events allows, safety data will be summarized using descriptive methodology. The incidence of treatment-emergent adverse events and serious adverse events will be presented by severity and by association with treatment as perceived by the investigator. Symptoms reported to occur prior to treatment with study drug will be distinguished from those reported as new or increased in severity during the trial. Safety parameters that will be assessed include laboratory tests, vital signs, electrocardiogram, body weight, immunogenicity, and injection-site reactions.

**Pharmacokinetics:** PK parameter estimates for LY3316531 will be calculated using standard noncompartmental methods of analysis. Parameters for estimation will include absolute bioavailability following SC administration, maximum observed drug concentration ( $C_{max}$ ), time to reach  $C_{max}$ , area under the concentration versus time curve (AUC) from time 0 to time of last measurable concentration ( $t_{last}$ ), AUC from time zero to infinity ( $AUC_{0-\infty}$ ), percentage extrapolated AUC from  $t_{last}$  to infinity, half-life, apparent clearance, and apparent volume of distribution. The dose proportionality of selected LY3316531 PK parameters will be examined across the dose range using a power model approach. Population PK analysis methods may be utilized if necessary.

**Pharmacodynamics:** Relationships between LY3316531 exposure and CGRP target engagement may be explored using graphical- and model-based approaches for all parts of the study (Parts A, B, and C). In patients with psoriasis (Part C), PD data obtained will be documented in the study report by dose, plasma drug concentrations, and time from dose. Figures showing values of potential PD markers versus time will be created for each dose, with a line for each patient. Absolute percentage change from baseline for all will be summarized by providing the mean, standard deviation, median, minimum, and maximum for each cohort and overall for each sample day/time combination and maximum over the entire study. Data may be log-transformed prior to summarizing if necessary. The interpatient and intrapatient variability in human PD responses may also be assessed if appropriate.

Exposure-response relationships for clinical activity measures in psoriasis (such as PASI score, static Physician Global Assessment, and body surface area) and safety endpoints will be investigated initially using graphical methods. Modeling approaches that relate exposure to the response at various time points or longitudinal models that relate the time course of exposure to the time course of response may be explored.

**Statistical:** PK/PD analyses will be conducted on data from all patients/subjects who receive at least 1 dose of the IP and have evaluable PK. Placebo data from all cohorts will be pooled across all dose-escalation cohorts for the purpose of analysis. Clinical activity and PD analyses will be conducted for all patients with psoriasis who receive the study drug (Part C only). Pharmacodynamic parameters, and their change from baseline, will be summarized at each applicable visit using descriptive statistics (number of subjects, mean, standard deviation, median, minimum, and maximum for continuous variables and number of subjects, frequency, and percent for categorical variables). No statistical inferences will be made and no control for multiplicity is planned. Additional analyses may be performed.

